4 TRIAL DESIGN

The study is an international, randomised, non-inferior, multicentre trial comparing traditional and transanal laparoscopic TME as the surgical treatment for rectal cancer. Patients will be accrued by all participating hospitals participating in the COLOR III study group (list of participating hospitals can be obtained through rectalcancersurgery.eu → 'COLOR III Trial'). All centres will follow a quality assurance program of the procedure itself and the data before data will be entered in the COLOR III trial. The COLOR III study group is an international group of surgeons with interest and expertise in minimally invasive colorectal surgery.

The first COLOR study started in 1997 and completed a large RCT in 2003 comparing laparoscopic to open surgery for colon cancer.^{36,37} Hereafter, many centres of this study group joined the COLOR II study group. The COLOR II study group recently completed a major RCT comparing laparoscopic to open TME in the treatment of rectal cancer.

The design involves allocation of all appropriate consecutive patients with mid or low rectum carcinoma to either of the two procedures at a randomisation ratio of 2:1 in favour of the TaTME procedure. Once eligibility has been established and patient details have been noted, the patient will be allocated to either transanal or laparoscopic TME. Assignment to one the two treatment groups will not be blinded. Randomisation will be performed by computer and will be balanced by T-stage, preoperative radiotherapy, height of the tumour, BMI and gender. Data will be analysed on 'intention to treat' basis in case patients are not subjected to the randomised treatment modality. Randomisation will be done through internet: rectalcancersurgery.eu (click 'COLOR III Trial → Professionals').

Included surgical procedures to obtain TME are 1. low anterior resection (LAR) with colorectal anastomosis 2. LAR with coloanal anastomosis

Excluded surgical procedures are extralevator abdominoperineal excision (ELAP) (i.e. patients with tumour in growth (more than 1/3) in the anal sphincter complex or levator ani.

Exclusion criteria are T4 tumours, T3 tumours with a suspected involved CRM after neoadjuvant therapy, patients with concomitant metastases or other malignancies, with malignancies in their medical history or with signs of acute mechanical obstruction by the tumour.

The trial will be stratified according to T-stage, preoperative radiotherapy, height of the tumour, BMI and gender.

Surgical Quality Assurance in COLOR III Trial

To ensure both surgical quality and centre capability to adhere to the study protocol, including the recruitment process and data collection, a Quality Assurance Protocol has been developed and will be applied before entering into the trial.

In order to ensure a standardised surgical quality an Operation Manual and a Competency Assessment Tool (CAT) for technical and oncological quality for laparoscopic and transanal TME within the scope of COLOR III have been developed. These will be used for surgeon selection into the trial and to measure adherence to agreed surgical quality standards during the trial. A Delphi methodology has been applied with a peer-nominated international group of expert colorectal consultants in the TaTME technique in order to develop a technical manual and operation logbook. A TaTME CAT was developed based on the results of the Delphi methodology. This tool has been tested for usability, reliability and validity prior to its implementation in the pre- and main trial phases.

Quality assurance before entering the trial

1. Centre Participating Criteria:

- Patient volume: minimum of 30 patients treated with rectal cancer per annum
- Number of surgeons: minimum of 2 colorectal surgeons, performing laparoscopic low anterior resection and the TaTME procedure independently.
- Training program: the centre has received training through a dedicated training program including cadaver training, and proctor supervised training. Centres with expertise in TaTME can be involved in hands on training and proctoring.

2. Trial entry criteria for quality assurance:

The participating centre will be required to recruit three consecutive cases, one laparoscopic low anterior and two TaTME to demonstrate its capability of collecting unedited operative videos. Baseline characteristics (eg. gender, age, tumour height, neoadjuvant therapy) need to be provide in order to have adequate assessment. The surgical performance will be assessed by two independent reviewers using competency assessment tool (CAT). Surgeons who do not satisfy the entry criteria will be required to gain more experience with the support from COLOR III training programme and re-assessed.

The data collected during this Surgical Quality Assurance Phase will not contribute to the main trial.

Since TaTME (and Laparoscopic TME) is already performed on a regular basis in the included hospitals, the surgical quality assurance prior to the COLOR III trial does not included randomisation nor the data is used in the COLOR III trial, collected surgical videos of patients before start of the COLOR III trial are accepted without specific COLOR III informed consent. This is only applicable for the three patients needed for the Surgical Quality Assurance, prior to the COLOR III trial. All other patients, included in the COLOR III trial will need to give informed consent before participation.

Quality assurance during the trial

1. The first three cases will be monitored extensively to assure that all the required data, complying with the COLOR III protocol including the treatment, is provided; clinical data including MRI and pathology will be reviewed centrally through the COLOR III secure digital case record form. A checklist will be used to measure the compliance. For each registered patient automatic generated reminders will be send to the local trial coordinators for providing requested information in order to limit potential delay in follow-up.
2. In order to monitor the surgical quality, participating surgeons will be required to use the developed operation notes to document the procedure and explain any deviation from the standardised technique. Surgeons will be required to submit an unedited video of every operation performed for both laparoscopic TME and TaTME; the videos will be assessed using the Competency Assessment Tool to evaluate the learning curve within the trial.

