14 STATISTICS AND DATA ANALYSIS

14.1 Sample size calculation

The primary endpoint is the local recurrence after 3 years. In laparoscopic TME the percentage of local recurrence is estimated 5%. A local recurrence increase of 4% is believed to be inferior. Based on this difference, sample size calculation has been done with a one-sided level of significance of 2,5% and a power of 80%. A total of 1104 patients is needed, 735 patients in the TaTME arm and 369 patients in the laparoscopic TME arm.

In this sample size calculation, additional postrandomisation analyses (drop-out, cross-over total 5%), is taken into account.

Randomisation will be stratified for

- T3a and less / T3b and more
- Downstaged with chemoradiotherapy: yes / no / NA
- Preoperative radiotherapy: yes / no
- Height of the tumour: 0-2.0cm / 2.1-5.0cm / 5.1-10cm
- Gender: male / female
- BMI \leq 30.0 / BMI $>$ 30.0

The randomisation will be executed in such a way that concealment of allocation for the indicating surgeon is guaranteed.

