14.2 Statistical analysis plan

Baseline numerical data will be described in means, standard deviations or medians and interquartile ranges, baseline categorical data will be displayed in percentages. All comparative analyses will be conducted on an 'intention to treat' basis. Consequently, patients who are randomised to TaTME and converted to a laparoscopic or open TME, will be analysed in the TaTME group. Patients who are randomised to a laparoscopic resection and converted to TaTME or open TME, will be analysed in the laparoscopic group. Ninety days postoperative mortality, pathological resection margin and complication rates will be compared using the Chi-square test or an exact test if necessary. Local recurrence rate, disease-free and overall survival will be compared using the Log-rank test. Exploratory analysis of the prognostic effects of various baseline factors on disease-free survival will be carried out through multivariate Cox-regression. Apart from intention to treat analyses, per protocol analyses will be applied.

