15.2 Data collected at randomisation

At randomisation, the clinician will be asked to give the following information through the internet:

- Eligibility criteria fulfilled?
- Randomising physician/surgeon
- Hospital (+ fax number)
- Type of planned surgery
- Patient: gender
- Patient: date of birth
- Clinical TMN stage

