15.3 Data collected during preoperative period

- ASA classification
- Length and weight
- Previous abdominal operations
- Medical history
- Date of diagnosis
- Location of the tumour on MRI
- Tumour characteristics
- Proposed type of resection
- Previous radiotherapy of the pelvis
- Preoperative (chemo)radiotherapy

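### The stratification factors differ between sections (five or six), the randomisation data list omits most of them, and the analysis section does not say whether it uses them

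*Protocol*

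**What the plan says.** **Factor lists.** Section 4 states "The trial will be stratified according to T-stage, preoperative radiotherapy, height of the tumour, BMI and gender". An earlier paragraph of section 4 and the Trial Summary (Statistics and randomisation) name the same five factors. Section 14.1 gives levels for these five and adds a sixth with three levels: "Downstaged with chemoradiotherapy: yes / no / NA".

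**Randomisation data.** Section 15.2 opens with "At randomisation, the clinician will be asked to give the following information through the internet". Its items are an eligibility check, the randomising physician, hospital, planned surgery, gender, date of birth and clinical TNM stage. The other inputs are in section 15.3, the preoperative list: "Location of the tumour on MRI", length and weight (from which BMI follows), and preoperative radiotherapy or chemoradiotherapy. Neither list names downstaging.

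**Analysis.** Section 14.2 assigns the log-rank test to local recurrence, disease-free survival and overall survival. For the short-term outcomes it says: "Ninety days postoperative mortality, pathological resection margin and complication rates will be compared using the Chi-square test or an exact test if necessary". It does not say whether either kind of test is stratified or adjusted. Its only covariate model is an exploratory Cox regression for disease-free survival. Section 14.3 plans subgroup analyses of local recurrence and margin involvement by tumour height.

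**The concern.** One allocation system cannot be built from two different factor lists. The difference matters in practice because the additional factor has three levels and multiplies the nominal cell count by three.

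Stratified allocation also needs the stratum values at the moment of allocation. If the randomisation form follows section 15.2, the computer has gender and a TNM stage, but not tumour height, BMI, radiotherapy or downstaging. Section 4 says that assignment is not blinded, so any stratum value recorded after allocation is recorded with the arm known. Tumour height is also a planned subgroup factor.

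Finally, if allocation is balanced on factors that the analysis does not use, the usual standard error still includes between-stratum variation that the design has removed. Some precision is then given up. The question is how much.

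**Working it through.** **1. Factors against randomisation inputs.**

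| Factor (levels in 14.1) | Summary and section 4 | 14.1 | Entered at randomisation (15.2) | Preoperative list (15.3) |
|---|---|---|---|---|
| T-stage, cut between T3a and T3b (2) | yes | yes | TNM stage; cut not named | – |
| Preoperative radiotherapy (2) | yes | yes | no | yes |
| Tumour height (3) | yes | yes | no | yes, as MRI location |
| Gender (2) | yes | yes | yes | – |
| BMI (2) | yes | yes | no | yes, as length and weight |
| Downstaged (3) | no | yes | no | not named |

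Section 15.2 omits three of the five factors, or four of the six.

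**2. Cell counts.** Five factors: 2×2×3×2×2 = 48 cells, and 1104/48 = 23 patients per cell. Six factors: 2×3×2×3×2×2 = 144 cells, with 1104/144 = 7.7 patients and 369/144 = 2.6 controls per cell. Some combinations cannot occur, so 144 is an upper bound. If NA means that no radiotherapy was given, radiotherapy and downstaging together form 3 combinations, and the count is 3×2×3×2×2 = 72.

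**3. The plan's sample size.** Inputs from 14.1: 5% recurrence with laparoscopic TME (assumed equal with TaTME), a 4-point margin ("A local recurrence increase of 4% is believed to be inferior"), one-sided 2.5%, power 80%, allocation 2:1, 5% loss. Evaluable controls = 0.05×0.95×1.5×(1.960+0.842)²/0.04² = 349.5. Total = 3×349.52 = 1048.6, and 1048.56/0.95 = 1103.75, which rounds up to 1104. The plan's figure reproduces.

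**4. Effect of leaving the factors out.** Take 698 and 350 evaluable patients (95% of 735 and 369). Let CV be the coefficient of variation of 3-year recurrence risk across strata. The documents do not give it, so a range is assumed. With p = 0.05:

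- usual variance per patient: p(1−p) = 0.0475
- variance within strata: 0.0475 − (CV×0.05)²
- standard error ratio: the square root of the first divided by the second

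Example, CV = 1.5: 0.0475 − 0.005625 = 0.041875, and √(0.0475/0.041875) = 1.065.

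Power without the strata is Φ((0.04 − 1.96×usual SE)/within-strata SE). With the strata it is Φ(0.04/within-strata SE − 1.96). Type I error is evaluated at 9% against 5%, with risks proportional across strata.

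| CV | SE ratio | Power without strata | Power with strata | One-sided type I error without strata |
|---|---|---|---|---|
| 0.2 | 1.001 | 80.0% | 80.1% | 0.0248 |
| 0.5 | 1.007 | 80.2% | 80.5% | 0.0239 |
| 1.0 | 1.027 | 80.7% | 82.1% | 0.0208 |
| 1.5 | 1.065 | 81.5% | 84.7% | 0.0159 |

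**5. The documents' own rates.** Table 2 in section 1 gives 3-year local recurrence of 6.5% for mid and 4.4% for low tumours (COLOR II subgroup). With equal shares (an assumption), mean risk is 0.0545, total variance is 0.0545×0.9455 = 0.05153, and between-group variance is 0.0105² = 0.00011. The standard error ratio is √(0.05153/0.05142) = 1.001.

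**6. Events available.** 0.05×1049 gives about 52 expected recurrences. That is about 1.1 per cell with 48 cells (52/48) and 0.4 with 144 (52/144). A main-effects model on the five factors needs 1+1+2+1+1 = 6 coefficients besides the arm.

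**The case against.** The strongest reply is that these are drafting gaps. Section 4 says that patient details are noted before allocation and that the computer balances on the five factors. The eligibility check in 15.2 already presupposes an MRI-measured height (5.1) and staging after any neoadjuvant treatment (5.2), and Appendix I defines T3a and T3b for the MRI report. Section 15.3 covers the preoperative period and does not say after randomisation. A reader might infer from 15.2 that the system cannot stratify on the missing factors. The text does not support that: it shows an incomplete list, not an inoperable system. What remains is that section 4 does not say which details are noted, so the gap stays open on paper.

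A reader might also infer that the arms will be unbalanced. Randomisation without strata still balances in expectation. For a factor present in half the patients, the standard error of the imbalance is √(0.25×(1/735+1/369)) = 3.2 percentage points.

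On the analysis, it is tempting to say that the plan ignores the factors. Section 14.2 does not exclude adjustment, and the statistical analysis plan, which is not at hand, may provide it. Nor are the factors shown to be the main drivers of recurrence: section 1 gives that place to an involved margin and a mesorectum that is not intact. A saving of 22 to 55 patients would need the factors to explain 2% to 5% of the variance (0.02×1104 and 0.05×1104), that is, a CV of about 0.62 to 0.97. The mid and low rates give 0.00011/0.05153 = 0.2%, about 2 patients for height alone. These objections limit the analysis point. They do not remove the conflict between the lists or the omission from 15.2.

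**Conclusion.** The inconsistency holds on the face of the protocol, and so does the incomplete randomisation list. Both concern allocation, so no later analysis document can settle them.

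The analysis point holds only as a request to state what is done. Over assumed CVs of 0.2 to 1.5, leaving the factors out makes the standard error 0.1% to 6.5% too large and costs 0.1 to 3.2 points of power. On the one pair of rates that the documents give, the inflation is about 0.1%. The error is in the safe direction: one-sided type I error is 0.016 to 0.025. If allocation turned out not to be balanced on the factors, the unadjusted test would simply keep its nominal level. A reader might infer that the sample size or the non-inferiority claim is endangered; neither is.

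The figures assume that the comparison is made on the difference scale of the sample size calculation, that allocation is balanced within strata, and that the CV lies in the stated range.

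**What to change.** 1. Give one identical list of factors with their levels in the Trial Summary, section 4 and 14.1, and decide whether downstaging is retained.
2. Add every retained factor to 15.2, including tumour height, BMI, radiotherapy and the T3a/T3b cut, with entry required before allocation. If downstaging is kept it needs a new field, because neither 15.2 nor 15.3 names it; it should not be assumed to be collected already.
3. State in 14.2 that the 3-year local recurrence difference is estimated with adjustment for the main effects of the randomisation factors, with the unadjusted result as a sensitivity analysis. A test stratified on every cell should be avoided, given the number of events expected.

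The cost is a few web-form fields, some wording and a little more analysis work. The first two changes matter most; the third is cheap but should not be expected to gain much.

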5 ELIGIBILITY CRITERIA

5.1 Inclusion criteria

- 1) Solitary adenocarcinoma rectal cancer within 10 cm from anal verge defined by MRI
- 2) Stage 1-3 according to the AJCC classification including downstaged tumours based on adequate imaging of the thorax and abdomen
- 3) Intention for LAR with colorectal anastomosis or with coloanal anastomosis
- 4) Suitable for elective laparoscopic surgical resection
- 5) Informed consent according to local requirements

5.2 Exclusion criteria

- 1) T3 tumour with margins less than 1 mm to the mesorectal fascia or T4 tumour, determined by MRI-scan (staged after (chemo)radiotherapy if applicable)
- 2) Intention for APR
- 3) Malignancy other than adenocarcinoma at histological examination
- 4) Patients under 18 years of age
- 5) Pregnancy
- 6) Previous prostate or rectal surgery (excluding local excision)
- 8) Signs of acute intestinal obstruction
- 9) Multiple colorectal tumours
- 10) Familial Adenomatosis Polyposis Coli (FAP), Hereditary Non-Polyposis Colorectal Cancer (HNPCC), active Crohn's disease or active ulcerative colitis
- 11) Planned synchronous abdominal organ resections
- 14) Other malignancies in medical history, except adequately treated basocellular carcinoma of the skin or in situ carcinoma of the cervix uteri
- 15) Absolute contraindication to general anaesthesia or prolonged pneumoperitoneum, as severe cardiovascular or respiratory disease (ASA class > III)

6 PERIOPERATIVE CARE AND EXAMINATIONS

6.1 Perioperative treatment strategies

Most international guidelines, including the current Dutch guideline for rectal cancer (2014), state that all patients diagnosed with rectal cancer should be discussed within a multidisciplinary oncological meeting preoperatively. Neoadjuvant radio- and/or chemotherapy should be considered in selected patients, according to local standards in multidisciplinary consultation. Changes in these protocols during the study period should be reported to and approved by the Protocol Committee.

6.2 Preoperative work-up

To exclude multiple tumours, a complete colonoscopy or CT-colonography is performed preoperatively, or within 3 months after surgery if primary colonoscopy/ CT-colonography was impossible due to a stenosing tumour. Biopsies of tumours are mandatory. Recto- or colonoscopy is performed to obtain histology and to optionally mark the distal border of the tumour prior to surgery. MRI-scan of the pelvis is conducted to assess its height from anal verge, its relation to surrounding structures and to estimate lymph node status (see Appendix I: MRI protocol and staging definitions). The radiologist should report the estimated distance between the tumour margin and the MRF. (appendix I MRI Protocol) Imaging of the thorax and abdomen is performed to screen for metastatic disease.

6.3 Preoperative care

Each centre should standardise preoperative care concerning:

- bowel preparation:

1. day before surgery: Moviprep and enema

2. day of surgery: enema

- deep venous thrombosis prophylaxis (low dose heparin and thrombo-prophylactic stockings during admittance)

- antibiotic prophylaxis

- enhanced recovery program

Preoperative care should be equal in both treatment arms throughout the duration of the trial.

6.4 Intraoperative care

Anaesthesia should be standardised by each participating centre for all patients in both treatment arms throughout the trial. The recommendation is not to use epidural anaesthesia.

Changes in anaesthetic protocols should apply to both treatment arms.

7 INVESTIGATIONAL PRODUCT

Not applicable.

8 NON-INVESTIGATIONAL PRODUCT

Not applicable.

9 SURGICAL PROCEDURE

9.1 TaTME (intervention arm)

The main definition of a Transanal TME is the dissection of (at least) the distal third from the transanal approach; The first intersphincteric dissection can be performed in an open fashion whereas the distal mesorectal dissection is performed with a platform with insufflation and minimal invasive instruments and camera to obtain optimal view of the anatomy and dissection planes. Detailed protocol based upon a Delphi method is shown in the appendix III.

The abdominal part of the procedure is performed laparoscopically with standard procedure; The proximal TME plane is opened from the abdominal site although the extent of abdominale and the extent of the transanal dissection is up to decision the surgical team and depends on the individual case. The formation of a diverting ileostomy is up to the decision of decision the surgical team and depends on the individual case.

9.2 Laparoscopic TME (control arm)

Complete laparoscopic dissection of the mesorectum is mandatory to qualify the procedure as a "laparoscopic TME". The level of transection of the inferior mesenteric artery is up to the surgeon's preference. Both right and left hypogastric nerves should be preserved. The splenic flexure should be mobilised when undue tension at the anastomoses is likely. Other aspects of the surgical procedure such as type of anastomoses, use of diverting ileostomy and drainage of surgical field are up to the discretion of the surgeon.

Included surgical procedures to obtain TME are 1. low anterior resection (LAR) with colorectal anastomosis 2. LAR with coloanal anastomosis

Excluded surgical procedures are abdominoperineal excision (APR) (i.e. patients with tumour in growth in the anal sphincter complex or levator ani more than 1/3).

9.3 Conversion

In TaTME conversion (to either laparoscopic or open TME) is defined as interruption of transanal TME due to technical difficulties or complications during transanal dissection, requiring completion of the majority of the TME using an abdominal approach. In laparoscopic TME conversion is defined when completion of the dissection of the mesorectum is performed through a traditional open abdominal or transanal approach. Conversion is determined by the surgeon in case of concerns about patient safety, technical difficulties, inability to complete the TME procedure adequately or associated conditions that require treatment.

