Interim analysis	Planned at 50% of the inclusion with regards to the sample size and conversions

TRIAL SUMMARY

Introduction and background

The quality of rectal cancer surgery has improved during the last decades with the total mesorectal excision (TME) technique, adaptation of laparoscopic surgery and extralevatory approach for abdominoperineal resection (APR). Nevertheless, surgery for mid and low rectal cancer is associated with relative high rates of conversions, permanent colostomies, and incomplete mesorectal excisions and relative high rates of circumferential resection margin (CRM) involvement resulting in significant number of local recurrences.

The transanal TME (TaTME) has been developed with use of laparoscopic single port platforms to improve the quality of the TME procedure in mid and low rectal cancer. In TaTME, the tumour is distally approached through the anus with laparoscopic instruments. In TaTME, the tumour is distally approached through the anus with laparoscopic instruments. Latest systematic review of cohort studies showed that the TaTME technique is feasible and facilitates difficult resections in the lower pelvis. A low conversion rate and more sphincter saving procedures are reported. Moreover the current data from cohort studies have shown that the TaTME procedure is safe and is associated with less conversions and less morbidity in experienced centres compared with laparoscopic TME.

. Before adaptation of the TaTME as standard surgical therapy for mid an low rectal cancer, a well-designed study is essential to demonstrate its efficacy and safety in a multicentre randomised setting. The primary concern is oncological safety in terms of local recurrence rate. Secondary concerns are conversion rate, permanent colostomy rate and safety in terms of pathology, morbidity and functional outcome.

Study design

The COLOR III trial is an international multicentre randomised study comparing short- and long term outcomes of TaTME and laparoscopic TME for rectal cancer. The design is non-inferiority compared to conventional laparoscopic surgery. The study will include a quality assessment phase before randomisation to ensure required competency level and uniformity of the new TaTME technique and the laparoscopic TME. During the trial the clinical data will be reviewed centrally to ensure uniform quality.

Endpoints

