The hypothesis is that TaTME will be non-inferior in mesorectum specimen quality and involved CRM and therefore will result in comparable rate of local recurrence. After TaTME which allows direct endoscopic visualisation we expect less morbidity due to less conversion rates and better anastomotic techniques. Moreover, the TaTME procedure will potentially enable more sphincter saving procedures. These expected results will have positive effect on functional outcome and health related quality of life.

FUNDING AND SUPPORT IN KIND

FUNDER(S) (Names and contact details of ALL organisations providing funding and/or support in kind for this trial)	FINANCIAL AND NON FINANCIAL SUPPORT GIVEN

KEY TRIAL CONTACTS

Trial Governors	Prof [name] (Chair Department of Surgery, VU University Medical Centre, Amsterdam) Prof [name] (Chief of Department of Gastrointestinal Surgery, Hospital Clinic, Barcelona) Prof [name] (Head of Division of Surgery, Imperial College, London)
Trial Co-ordinator	[name], [name]
Trial Contacts	[name], [name] VU University Medical Centre Department of Surgery [name], The Netherlands Email: [contact] [contact] [contact]
Protocol and Writing Committee	[name], [name], [name], [name], [name] , [name], [name], [name], [name], [name], [name], [name]
Statistician	[name]
COLOR III study group	All included centres; Follows

LIST OF CONTENTS

[figure not shown]
GENERAL INFORMATION	Page
TITLE PAGE	1
RESEARCH REFERENCE NUMBERS	2
SIGNATURE PAGE	3
TRIAL SYNOPSIS	4
TRIAL SUMMARY	5
FUNDING	7
KEY TRIAL CONTACTS	8
LIST OF CONTENTS	9
LIST OF ABBREVIATIONS	10
TRIAL FLOW CHART	12
STUDY PROTOCOL	
1. BACKGROUND	13
2. RATIONALE	16
3. OBJECTIVES AND OUTCOME MEASURES/ENDPOINTS	17
4. TRIAL DESIGN	19
5. ELIGIBILITY CRITERIA	22
6. PERIOPERATIVE CARE AND EXAMINATION	23
7. INVESTIGATIONAL PRODUCT	24
8. NON-INVESTIGATIONAL PRODUCT	25
9. SURGICAL PROCEDURE	26
10. (HISTO)PATHOLOGY	28
11. POSTOPERATIVE TREATMENT	30
12. FOLLOW-UP	31
13. RECURRENT DISEASE	32
14. STATISTICS AND DATA ANALYSIS	33
15. ADMINISTRATIVE ASPECTS, MONITORING AND PUBLICATION	34
16. SAFETY REPORTING	37
17. ETHICAL AND REGULATORY CONSIDERATIONS	43
18. REFERENCES	45
19. APPENDICES	48

LIST OF ABBREVIATIONS

AE	Adverse Event
APR	Abdominoperineal Resecton
AR	Adverse Reaction
cCRM	Clinical Circumferential Resection Margin
CI	Chief Investigator
CRF	Case Report Form

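### Section 9.3 defines conversion differently in the two arms, so the rates are not comparable and conversion to open surgery is under-counted in the TaTME arm

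*Protocol*

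**What the plan says.** Protocol section 9.3 has one definition per arm.

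- **TaTME:** "interruption of transanal TME due to technical difficulties or complications during transanal dissection, requiring completion of the majority of the TME using an abdominal approach". The target may be laparoscopic or open TME.
- **Laparoscopic TME:** conversion occurs when "completion of the dissection of the mesorectum is performed through a traditional open abdominal or transanal approach".

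A closing sentence covers both arms: "Conversion is determined by the surgeon in case of concerns about patient safety, technical difficulties, inability to complete the TME procedure adequately", or when an associated condition needs treatment.

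Section 9.1 describes TaTME as a two-part operation. "The abdominal part of the procedure is performed laparoscopically with standard procedure", and within that part "The proximal TME plane is opened from the abdominal site". How much is dissected from each side is left to the team.

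Conversion has a visible role in the protocol. The trial summary names its rate among the secondary concerns, and the hypothesis states that "we expect less morbidity due to less conversion rates". The background sets no conversions in the group's TaTME pilot against 16% in COLOR II. The synopsis describes the interim analysis as "Planned at 50% of the inclusion with regards to the sample size and conversions". Conversion is absent from the endpoint list in section 3.3. The operative data listed in section 15.4 include reasons for conversion but not the phase in which it happened.

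**The concern.** The TaTME definition has three conditions: the transanal part is interrupted, the trouble arises during transanal dissection, and most of the TME is then done from the abdomen. The laparoscopic definition has no condition on phase, cause or share. The same event, opening the abdomen to complete the mesorectal dissection, can therefore be a conversion in one arm and not in the other.

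The comparison of conversion rates is at stake, both at the interim look and in the final report. Fewer conversions is one of the reasons given for expecting less morbidity with TaTME. Treatment is not blinded and the surgeon determines conversion, so the written definition is the main protection for a fair comparison. If it counts different events by arm, a difference in open conversion can appear where the abdomen was opened equally often.

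**Working it through.** **Step 1. The two definitions applied to the same events (sections 9.1 and 9.3).**

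| Event | TaTME arm | Laparoscopic arm |
|---|---|---|
| Abdomen opened to complete the mesorectal dissection in the abdominal phase; transanal part goes ahead | Not counted | Counted (the whole dissection is abdominal) |
| Transanal part interrupted; less than the majority of the TME then completed by open surgery | Not counted | No equivalent threshold; any open completion counts |
| Transanal part interrupted; majority then completed by open surgery | Counted | Not applicable |
| Transanal part interrupted; majority then completed laparoscopically, nothing opened | Counted | Not applicable |
| Laparoscopic dissection completed transanally | Not applicable | Counted |
| Abdomen opened only for another step, such as flexure mobilisation | Not counted | Not counted |

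The first two rows lower the TaTME count of open conversions. The fourth raises the overall TaTME count and the fifth raises the overall laparoscopic count.

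**Step 2. Arm sizes.** The planned sizes are 735 and 369 (section 14.1). They reproduce from the stated inputs (5% in both arms, margin 4 points, one-sided 2.5%, power 80%, 2:1):

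n(control) = (1.960 + 0.842)² × 0.05 × 0.95 × (1 + 1/2) / 0.04² = 349.5, so 350, with 700 for TaTME.

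With 5% dropout, 350/0.95 = 368.4, so 369, and 1050/0.95 = 1105.3, so 1106 in total against 1104 stated. For the interim look, about half of each arm is used: 368 and 184.

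**Step 3. Conversion to open surgery, with no true difference.** Let q be the true rate of opening to complete the mesorectal dissection, equal in both arms, and f the share of TaTME openings that fall outside the TaTME wording. Then

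- laparoscopic rate = q
- TaTME rate = q(1 − f)
- undercount = q × f.

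The value q = 16% is the COLOR II conversion figure quoted in the background, used here as an assumed opening rate. The values q = 10% and 5%, and every value of f, are assumptions with no source in the documents.

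Chance of a significantly lower TaTME rate, two-sided 5% test: Φ((d − 1.96 s₀)/s₁). Here d is the difference, s₁ the unpooled standard error, and s₀ the pooled standard error (or s₁ for an unpooled test).

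Worked case, q = 16% and f = 50%, so 8% against 16% and d = 0.08:

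- pooled rate = (735 × 0.08 + 369 × 0.16)/1104 = 0.1067
- s₀ = √(0.1067 × 0.8933 × (1/735 + 1/369)) = 0.0197
- s₁ = √(0.08 × 0.92/735 + 0.16 × 0.84/369) = 0.02155
- unpooled: Φ(0.08/0.02155 − 1.96) = Φ(1.75) = 96%
- pooled: Φ((0.08 − 1.96 × 0.0197)/0.02155) = Φ(1.92) = 97%.

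The same formula gives (unpooled to pooled):

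| q | f | Rates read | Full size | Interim |
|---|---|---|---|---|
| 16% | 25% | 12% v 16% | 43–46% | 24–26% |
| 16% | 50% | 8% v 16% | 96–97% | 75–80% |
| 10% | 25% | 7.5% v 10% | 27–30% | 16–18% |
| 10% | 50% | 5% v 10% | 81–86% | 52–59% |
| 5% | 25% | 3.75% v 5% | 15–17% | 10–11% |
| 5% | 50% | 2.5% v 5% | 50–58% | 28–35% |

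**Step 4. The overall 9.3 rate.** Let s be the rate of TaTME-to-laparoscopic switches and t the rate of laparoscopic-to-transanal switches. The TaTME rate is q(1 − f) + s and the laparoscopic rate is q + t, so the expected difference is s − qf − t. Its sign depends on three quantities that the documents do not give.

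With q = 16%, f = 50%, t = 0 and the pooled test at full size:

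- s = 0: 8% v 16%, chance 97%
- s = 4%: 12% v 16%, chance 46%
- s = 6%: 14% v 16%, chance 15%
- s = 8%: no expected difference
- s = 10%: 18% v 16%, sign reversed.

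With f = 25%, s = 4% already cancels the difference.

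**The case against.** A reader might infer that section 9.3 builds in a lower TaTME conversion rate overall. The documents do not support that. The TaTME definition is narrower on openings but wider elsewhere, since an operation finished laparoscopically with nothing opened still counts. Step 4 shows that a modest rate of such switches shrinks, cancels or reverses the difference, while transanal completions in the laparoscopic arm push the other way. This objection stands: only the bias in conversion to open surgery has a known direction.

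Four further objections can be made.

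- **Size.** The uncounted share has no source in the documents, so the percentages illustrate and do not estimate. This stands.
- **Reach.** Section 3.3 does not list conversion, section 14.2 names no test for it, and neither the synopsis nor the monitoring board charter sets a conversion threshold. A false significant result presupposes a test that this protocol does not specify. This stands, and it limits the consequence. The interim look and the hypothesis still invite the comparison.
- **Recoverability.** Reasons for conversion are recorded, operation notes must explain deviations, and unedited video of every operation is required (section 4), with pelvic dissection from both platforms assessed (Appendix III). Many uncounted openings could be found later. This stands in part: phase is not among the listed data, and an opening that is not classed as a conversion need not generate a recorded reason.
- **Inherent difference.** Abandoning a hybrid transanal operation is not the same event as abandoning a laparoscopic one, so an arm-specific definition is legitimate. That is a reason to keep the section 9.3 wording for description, not to compare arms on it.

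The closing sentence of section 9.3 could be read as widening both definitions. It lists who decides and why, but does not say that opening in the abdominal phase of TaTME counts.

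**Conclusion.** The concern holds for comparability and for conversion to open surgery. The two section 9.3 rates measure different things. Conversion to open surgery is under-counted in the TaTME arm by q × f: 4 points at q = 16% with a quarter uncounted, and 8 points with half uncounted. The asymmetry is certain from the text; its size is not known, because the documents give no value for f. For the overall rate, the direction of bias is unknown.

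The local recurrence analysis is by intention to treat and does not use conversion status to assign patients to arms, so the primary result is unaffected. Sections 9.1 and 9.3 should be reconciled on what counts.

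**What to change.** This is a cheap improvement.

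- Add one comparative outcome counted identically in both arms: unplanned change to open abdominal surgery to complete the mesorectal dissection, in any phase and for any cause.
- List it in section 3.3, and use it for the interim look at conversions and for the between-arm comparison.
- Record on the case report form the phase of every such opening, whether or not it meets section 9.3.
- Keep the section 9.3 wording as an arm-specific failure of the assigned approach, reported descriptively with the reasons already collected under section 15.4. Show TaTME-to-laparoscopic and laparoscopic-to-transanal switches separately.

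The cost is one definition and one form item. The TaTME rate may look less favourable than in the published series. The change affects measurement only and alters no surgical decision.
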